#### 11.1.3 Methods for Evaluation of Measurable Disease

All measurements should be taken and recorded in metric notation using a ruler or calipers. All baseline evaluations should be performed as closely as possible to the beginning of treatment and never more than 4 weeks before the beginning of the treatment.

The same method of assessment and the same technique should be used to characterize each identified and reported lesion at baseline and during follow-up. Imaging-based evaluation is preferred to evaluation by clinical examination unless the lesion(s) being followed cannot be imaged but are assessable by clinical exam.

**Clinical lesions** Clinical lesions will only be considered measurable when they are superficial (e.g., skin nodules and palpable lymph nodes) and  $\geq 10$  mm diameter as assessed using calipers (e.g., skin nodules). In the case of skin lesions, documentation by color photography, including a ruler to estimate the size of the lesion, is recommended.

**Chest x-ray** Lesions on chest x-ray are acceptable as measurable lesions when they are clearly defined and surrounded by aerated lung. However, CT is preferable.

**Conventional CT and MRI** This guideline has defined measurability of lesions on CT scan based on the assumption that CT slice thickness is 5 mm or less. If CT scans have slice thickness greater than 5 mm, the minimum size for a measurable lesion should be twice the slice thickness. MRI is also acceptable in certain situations (e.g. for body scans).

Use of MRI remains a complex issue. MRI has excellent contrast, spatial, and temporal resolution; however, there are many image acquisition variables involved in MRI, which

greatly impact image quality, lesion conspicuity, and measurement. Furthermore, the availability of MRI is variable globally. As with CT, if an MRI is performed, the technical specifications of the scanning sequences used should be optimized for the evaluation of the type and site of disease. Furthermore, as with CT, the modality used at follow-up should be the same as was used at baseline and the lesions should be measured/assessed on the same pulse sequence. It is beyond the scope of the RECIST guidelines to prescribe specific MRI pulse sequence parameters for all scanners, body parts, and diseases. Ideally, the same type of scanner should be used and the image acquisition protocol should be followed as closely as possible to prior scans. Body scans should be performed with breath-hold scanning techniques, if possible.

Ultrasound Ultrasound is not useful in assessment of lesion size and should not be used as a method of measurement. Ultrasound examinations cannot be reproduced in their entirety for independent review at a later date and, because they are operator dependent, it cannot be guaranteed that the same technique and measurements will be taken from one assessment to the next. If new lesions are identified by ultrasound in the course of the study, confirmation by CT or MRI is advised. If there is concern about radiation exposure at CT, MRI may be used instead of CT in selected instances.

Endoscopy, Laparoscopy The utilization of these techniques for objective tumor evaluation is not advised. However, such techniques may be useful to confirm complete pathological response when biopsies are obtained or to determine relapse in trials where recurrence following complete response (CR) or surgical resection is an endpoint.

Tumor markers Tumor markers alone cannot be used to assess response. If markers are initially above the upper normal limit, they must normalize for a patient to be considered in complete clinical response.

Cytology, Histology These techniques can be used to differentiate between partial responses (PR) and complete responses (CR) in rare cases (e.g., residual lesions in tumor types, such as germ cell tumors, where known residual benign tumors can remain).

The cytological confirmation of the neoplastic origin of any effusion that appears or worsens during treatment when the measurable tumor has met criteria for response or stable disease is mandatory to differentiate between response or stable disease (an effusion may be a side effect of the treatment) and progressive disease.

#### 11.1.4 Response Criteria

##### **Evaluation of Target Lesions**

Complete Response (CR): Disappearance of all target lesions. Any pathological lymph nodes (whether target or non-target) must have reduction in short axis to <10 mm.

Partial Response (PR): At least a 30% decrease in the sum of the diameters of target lesions, taking as reference the baseline sum diameters.

Progressive Disease (PD): At least a 20% increase in the sum of the diameters of target lesions, taking as reference the smallest sum on study (this includes the baseline sum if that is the smallest on study). In addition to the relative increase of 20%, the sum must also demonstrate an absolute increase of at least 5 mm. (Note: the appearance of one or more new lesions is also considered progressions).

Stable Disease (SD): Neither sufficient shrinkage to qualify for PR nor sufficient increase to qualify for PD, taking as reference the smallest sum diameters while on study.

### **Evaluation of Non-Target Lesions**

Complete Response (CR): Disappearance of all non-target lesions and normalization of tumor marker level. All lymph nodes must be non-pathological in size (<10 mm short axis).

Note: If tumor markers are initially above the upper normal limit, they must normalize for a patient to be considered in complete clinical response.

Non-CR/Non-PD: Persistence of one or more non-target lesion(s) and/or maintenance of tumor marker level above the normal limits.

Progressive Disease (PD): Appearance of one or more new lesions and/or *unequivocal progression* of existing non-target lesions. *Unequivocal progression* should not normally trump target lesion status. It must be representative of overall disease status change, not a single lesion increase.

Although a clear progression of “non-target” lesions only is exceptional, the opinion of the treating physician should prevail in such circumstances, and the progression status should be confirmed at a later time by the review panel (or Principal Investigator).

### **Evaluation of Best Overall Response**

The best overall response is the best response recorded from the start of the treatment until disease progression/recurrence (taking as reference for progressive disease the smallest measurements recorded since the treatment started). The patient's best response assignment will depend on the achievement of both measurement and confirmation criteria

### **For Patients with Measurable Disease (*i.e.*, Target Disease)**

Target Lesions	Non-Target Lesions	New Lesions	Overall Response
CR	CR	No	CR
CR	Non-CR/Non-PD	No	PR
CR	Not evaluated	No	PR
PR	Non-CR/Non-PD/not evaluated	No	PR
SD	Non-CR/Non-PD/not evaluated	No	SD
PD	Any	Yes or No	PD

Any	PD***	Yes or No	PD
Any	Any	Yes	PD
* See RECIST 1.1 manuscript for further details on what is evidence of a new lesion.			
** As response rate is not the primary endpoint of the study, no confirmatory imaging evaluation is required.			
*** In exceptional circumstances, unequivocal progression in non-target lesions may be accepted as disease progression.			

Note: Patients with a global deterioration of health status requiring discontinuation of treatment without objective evidence of disease progression at that time should be reported as “symptomatic deterioration.” Every effort should be made to document the objective progression even after discontinuation of treatment.
			

### For Patients with Non-Measurable Disease (i.e., Non-Target Disease)

Non-Target Lesions	New Lesions	Overall Response
CR	No	CR
Non-CR/non-PD	No	Non-CR/non-PD*
Not all evaluated	No	Not evaluated
Unequivocal PD	Yes or No	PD
Any	Yes	PD
* ‘Non-CR/non-PD’ is preferred over ‘stable disease’ for non-target disease since SD is increasingly used as an endpoint for assessment of efficacy in some trials so to assign this category when no lesions can be measured is not advised		

#### 11.1.5 Duration of Response

Duration of response will be assessed in patients with measurable disease.

Duration of overall response: The duration of overall response is measured from the time measurement criteria are met for CR or PR (whichever is first recorded) until the first date that recurrent or progressive disease is objectively documented (taking as reference for progressive disease the smallest measurements recorded since the treatment started).

The duration of overall CR is measured from the time measurement criteria are first met for CR until the first date that progressive disease is objectively documented.

Duration of stable disease: Stable disease is measured from the start of the treatment until the criteria for progression are met, taking as reference the smallest measurements recorded since the treatment started, including the baseline measurements.

#### 11.1.6 Progression-Free Survival

PFS is defined as the duration of time from start of treatment to time of progression or death,

whichever occurs first. Patients without an event will be censored at the end of 2 year follow-up.

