## 5.5 Duration of follow up

Once the treatment with AZD1775 is completed, patients will have an end of treatment visit 28 days  $\pm$  7 days after their last dose of AZD1775. After that, they will be followed to evaluate toxicity or disease relapse every 4 months ( $\pm$  2 weeks) for 2 years, until any of the criteria mentioned in [section 5.6](#) apply. Patients removed from protocol therapy for unacceptable adverse event(s) will be followed until resolution or stabilization of the adverse event.

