## 5.6 Criteria for removal from study

Patient will be removed from the study when any of the following criteria listed below applies:

- Disease progression (clinical or radiological)
- Patient death
- Patient withdraws consent
- 2-year follow up complete
- Termination of study by Principal Investigator, Sponsor, or Regulatory Authorities

The reason for study removal and the date the patient was removed must be documented in the Case Report Form.

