## 6.1 Dose delays/interruptions

- No more than two AZD1775 or one cisplatin dose reduction for toxicity will be permitted. If the toxicity persists despite the reductions, the patient will be removed from the trial.
- Patients will be removed from the protocol therapy for:
- Any acute toxicity that persists despite two AZD1775 or one cisplatin dose reduction

- Any acute toxicity requiring a delay in cisplatin, AZD1775 and/or radiotherapy > 2 weeks, unless approved by the Principal Investigator or Senior Protocol Investigator.
- Any acute Grade 4 non-hematological toxicity
- For electrolyte disturbances, patients will be discontinued if the electrolyte abnormality persists more than 48 hours despite optimal treatment
- Patients removed from the trial because of acute toxicity will continue treatment for cervix cancer with either radiotherapy alone or RT-CT, at the discretion of the responsible medical and radiation oncologists.
- RT is the primary therapeutic modality in this treatment regimen. There will be no delays or modifications to the planned course of radiotherapy except in exceptional circumstances, at the discretion of the treating radiation oncologist, where acute toxicity persists after appropriate cisplatin and/or AZD1775 dose reductions. For toxicity dose modifications, or delays, AZD1775 will be modified first, followed by cisplatin. Radiation will be maintained on schedule if possible. If a situation arises where dose modification or delay is necessary and not captured by the dose adjustment criteria, the decision on dose adjustment will be made by the Senior Scientific Investigator and Principal Investigator and documented.
- In case of grade 3 non-hematological DLTs or any hematological DLTs, treatment could be resumed if the toxicity is resolved to:
  - Grade 2 if the DLT was radiotherapy-induced dermatitis.
  - Tolerable grade 2 (in areas not included in the radiotherapy volume)
  - Grade 1 or baseline for the remaining DLT toxicitiesThe treatment will be resumed with appropriate dose reduction(s) of the study drugs as described in [section 6.2](#)
- An exception would be made for the following grade 4 non-hematological toxicities, classically associated to cisplatin treatment after which cisplatin will be permanently discontinued, but AZD1775 could be resumed following the criteria in [Table 6-9](#).
  - Grade 4 tinnitus
  - Grade 3 and 4 hearing loss
  - Grade 3 and 4 neurotoxicity

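### The only PFS censoring rule carries every event-free patient to the end of the 2-year follow-up, including those who leave early, so the PFS curve can be raised but never lowered

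*Combined protocol and SAP*

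**What the plan says.** Section 11.1.6 measures PFS from start of treatment to progression or death and then gives one censoring rule: "Patients without an event will be censored at the end of 2 year follow-up". Section 13.3.1, which covers analysis of the secondary clinical endpoints, adds no censoring rule and names no survival-curve estimator. It names Cox regression among the methods for studying predictors of outcome.

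Other sections foresee patients leaving without an event before that point:

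- Section 5.5 schedules visits every 4 months "for 2 years, until any of the criteria mentioned in" Section 5.6 applies.
- Section 5.6 lists "Patient withdraws consent" and "Termination of study by Principal Investigator, Sponsor, or Regulatory Authorities" as criteria in their own right, apart from "2-year follow up complete". It also states: "The reason for study removal and the date the patient was removed must be documented in the Case Report Form". Nothing makes that date the censoring date.
- Section 6.1 says of toxicity after dose reductions: "If the toxicity persists despite the reductions, the patient will be removed from the trial". Its list for the same situation speaks instead of removal from protocol therapy.
- Section 5.5 adds: "Patients removed from protocol therapy for unacceptable adverse event(s) will be followed until resolution or stabilization of the adverse event". It does not say whether disease follow-up goes on for these patients.

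Loss to follow-up is not mentioned.

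**The concern.** A censoring time should mark the last point at which a patient was known to be event-free. Section 11.1.6 uses one fixed point for everyone without an event. A patient who withdraws at month 5 would be counted as at risk and progression-free until the end of the 2-year follow-up. Any progression after exit is never seen, yet the patient stays in the denominator for every later event.

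At stake is the secondary objective of obtaining preliminary information on PFS (Section 1.2). The recommended phase II dose rests on DLTs and is not affected. The error in the curve has one direction, and a larger sample does not remove it. In a Cox predictor analysis the direction is not fixed: if early exit is more common in one group, the hazard ratio can move either way.

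**Working it through.** The plan states no PFS rate, event count or dropout rate, so it offers no figure to reproduce. The check has four parts: direction, a worked example, size under assumed rates, and the Cox analysis.

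**Inputs from the documents.** Total enrolment is 9 to 33 (Section 13.2), with 15 patients at the recommended dose (Table 5-3). Follow-up is up to 2 years after the End of Treatment visit (Section 10, note k), and that visit falls 28 ± 7 days after the last AZD1775 dose. With the last dose at about day 33, 33 + 28 = 61 days, or about 2 months, so follow-up ends about 26 months after start of treatment.

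**Assumptions.** True 2-year PFS *S*, proportion *q* leaving event-free by 24 months, exponential times for both, and a Kaplan-Meier curve.

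**Direction.** The estimate is the product of (1 − d/n) over event times. Moving a censoring time later leaves every event time and every d unchanged and can only increase n at later events. Each factor therefore rises or stays the same. In 24,000 simulated data sets (n = 15 and n = 33, with and without tied times), the literal curve was never below the curve with censoring at exit.

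**Worked example (assumed data).** Fifteen patients, events at months 8, 10, 12, 16 and 20, and k event-free leavers at month 6. The literal rule gives 10/15 = 0.667 for any k. Censoring at exit gives (10 − k)/(15 − k):

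| k | Censored at exit | Literal rule | Difference |
|---|---|---|---|
| 1 | 9/14 = 0.643 | 0.667 | +0.024 |
| 2 | 8/13 = 0.615 | 0.667 | +0.051 |
| 3 | 7/12 = 0.583 | 0.667 | +0.083 |
| 5 | 5/10 = 0.500 | 0.667 | +0.167 |

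If the leavers go at month 21, after the last event, both rules give 0.667.

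**Expected size.** Let λ = −ln(S)/24 and μ = −ln(1 − q)/24. Under the literal rule nobody is censored before 24 months, so the expected estimate is

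1 − [λ/(λ + μ)] × [1 − exp(−24(λ + μ))].

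For S = 0.60 and q = 0.20: 24λ = 0.511 and 24μ = 0.223, so 1 − (0.511/0.734) × (1 − 0.480) = 0.638, which is 3.8 points too high. The full set, in percentage points:

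| True 2-year PFS | q = 5% | 10% | 20% | 30% |
|---|---|---|---|---|
| 50% | +1.1 | +2.3 | +4.6 | +7.1 |
| 60% | +0.9 | +1.9 | +3.8 | +5.8 |
| 70% | +0.7 | +1.4 | +2.9 | +4.5 |

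Uniform exit times give nearly the same (S = 60%: +0.9, +1.8, +3.7, +5.5). Simulation with uniform exit times at n = 15, S = 0.60 and q = 0.20 gives a mean of 0.635 under the literal rule and 0.598 with censoring at exit.

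**One very early exit.** If one of 15 patients leaves at month 1, the bias is (1/15) × (S^(1/24) − S). At S = 0.60 this is (0.979 − 0.600)/15 = 2.5 points; at 0.50 it is 3.1 and at 0.70 it is 1.9.

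**How often nothing changes.** One event-free exit at a uniform time among 15 patients leaves the 24-month estimate unchanged in about 13%, 17% and 23% of simulated trials at S = 50%, 60% and 70%.

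**Cox.** Two groups with true hazard ratio 1 (200,000 simulated patients each, follow-up to 26 months) and early exit in one group only. The literal rule gives 0.88 or 1.14 with 20% exit and 0.82 or 1.22 with 30% exit, depending on which group loses patients. Censoring at exit gives 0.99 to 1.01.

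**Scale.** The exact 95% confidence interval for 9 of 15 event-free is 32% to 84%.

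**The case against.** The strongest reply is that the rule need not be read literally. Section 5.5 ends follow-up when a Section 5.6 criterion applies, so the end of follow-up could mean each patient's own end within the 2 years, and the removal date is already recorded. That reading is possible, and a careful analyst might adopt it. It does not settle the matter: Section 11.1.6 names the 2-year point, and Section 5.6 lists completion of the 2 years as a separate item from withdrawal and termination.

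The toxicity route is less certain than the other two. Section 5.6 does not list toxicity as a reason for leaving the study, Section 5.4 treats it as a reason to stop treatment, and Section 6.1 uses both expressions. The month-1 figure therefore shows what that route could do, not what should be expected. The case for a fix does not need it, because withdrawal and termination are enough.

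All exit rates and the one-sided Cox contrasts are assumed, and the bias is small beside the sampling error. Both points stand, and they limit how much weight the issue deserves.

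Finally, the calculations compare the literal rule with censoring at exit, whereas the proposed rule censors at the last disease assessment, which may be up to about 4 months earlier. The direction still holds, because the last assessment is never later than exit.

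**Conclusion.** The concern holds. The plan's single PFS censoring rule has no provision for event-free patients who leave early. Followed as written, it counts unobserved time as event-free, and a Kaplan-Meier curve is then raised or unchanged, never lowered. The direction follows from the estimator and needs no assumption about exit rates. The size does: for true 2-year PFS of 50% to 70% it runs from zero with no early exit to between 4.5 and 7.1 points with 30% exit. Cox hazard ratios can be distorted in either direction when exit differs between groups.

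This should be corrected before analysis. It concerns a secondary, exploratory endpoint and leaves the dose recommendation untouched.

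**What to change.** Replace the censoring sentence in Section 11.1.6 with wording such as:

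> Patients without progression or death are censored at the date of their last disease assessment (imaging or clinical follow-up visit) documenting no progression, or at start of treatment if there is none, and no later than the end of the 2-year follow-up. This applies to withdrawal, removal for toxicity without further disease follow-up, loss to follow-up, study termination and patients still in follow-up at the data cut. PFS is estimated by Kaplan-Meier.

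If the authors already mean each patient's own end of follow-up, the section should say so.

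Clinical visits should count as assessments because Study Calendar note q allows progression to be documented clinically. Note f requires RECIST measurements after baseline only at end of treatment, 4 months after radiotherapy, and when a patient comes off study within 4 months after planned treatment. Note h asks for radiologic documentation when a patient is removed for progression, so notes h and q should be reconciled. Sections 5.5, 5.6 and 6.1 should be reconciled on whether patients removed for toxicity remain in disease follow-up.

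The data-cut clause matters if the 20 to 24 month study duration in Section 13.2 includes follow-up, since each patient's follow-up alone ends at about 26 months. If that figure covers accrual only, the clause does no harm.

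The cost is a few sentences. Visits every 4 months are already scheduled, and removal dates and reasons are already collected. Reported PFS may be slightly lower with a wider interval, and the analysis will assume that early exit is unrelated to prognosis.

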## **12. STUDY OVERSIGHT AND DATA REPORTING / REGULATORY REQUIREMENTS**

Adverse event lists, guidelines, and instructions for AE reporting can be found in [Section 7.0](#) (Adverse Events: List and Reporting Requirements).

### **12.1 Study Oversight**

This protocol is monitored at several levels, as described in this section. The Protocol Principal Investigator is responsible for monitoring the conduct and progress of the clinical trial, including the ongoing review of accrual, patient-specific clinical and laboratory data, and routine and serious adverse events; reporting of expedited adverse events; and accumulation of reported adverse events from other trials testing the same drug(s). The Protocol Principal Investigator and statistician have access to the data at all times through the CTMS web-based reporting portal.

For the Phase 1 portion of this study, all decisions regarding dose escalation/expansion/de-escalation require sign-off by the Protocol Principal Investigator through the CTMS/IWRS. In addition, the Protocol Principal Investigator will have at least monthly, or more frequently, conference calls with the Study Investigators and the CTEP Medical Officer(s) to review accrual, progress, and adverse events and unanticipated problems.

All Study Investigators at participating sites who register/enroll patients on a given protocol are responsible for timely submission of data via Medidata Rave and timely reporting of adverse events for that particular study. This includes timely review of data collected on the electronic CRFs submitted via Medidata Rave.

All studies are also reviewed in accordance with the enrolling institution's data safety monitoring plan.

